³Visit 5 should be no more than 7 days after Visit 4. Where the patient does not meet the additional inclusion criteria 13 and 14 based on lab tests performed at Visit 4, the eGFR and potassium cannot be re-tested and the patient should permanently discontinue the study. In case of unexpected delay of Visit 5, a repeat safety sample must be taken to obtain potassium and eGFR results needed to confirm eligibility for the Treatment Period.

⁴In case a patient needs or wishes to terminate all trial treatment prematurely and if the patient agrees, the patient should undergo the procedures for End of Treatment (EoT). Please see [section 6.2.5](#) for details.

⁵Follow-up Visit 1 (FU1) must always take place at least 7 days after the EoT visit.

⁶These visits can either be performed at the Investigational site or at the patient's home. All local approvals for this must be in place and confirmed by the sponsor. Consent for home visits must also be obtained from the patient. See [section 6.2.2](#) for further details.

⁷There are various ways that Telemedicine contacts (phone call or video call) can be used during this trial:

1. Telemedicine contact to provide support for patient's urine sampling. Before the patient does their first UACR sampling at home the investigational site staff should contact the patient to ensure the patient is comfortable with the sampling process. The other timepoints marked as '(X)' are suggested times to contact the patient if they are shipping samples directly from home to ensure they understand the instructions given to them. The site may, at their discretion, offer support with further home sampling according to the individual needs of a patient.
2. Visit 3 must be performed as telemedicine contact for all patients, unless they prefer to come to the trial site instead.
3. Phone/ video calls may also take place at any other time if needed to support the patient.

⁸Informed consent must be obtained before the first screening assessment. It can be obtained on the day of the screening visit or within 4 weeks prior to the first screening assessment. The consent discussion should include showing the patient the home sampling kits and explaining this procedure.

⁹All ECGs will be done prior to the daily dose and evaluated by the investigator or a designee. See [section 5.2.4](#).

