²⁰To confirm eligibility, at visit 1, UACR measured in spot urine (midstream urine sample) by the central laboratory will be used. Should the first test for UACR at screening not match inclusion criteria due to UACR variability, this can be repeated once. If the second result does not meet the eligibility criteria the patient should be screen failed.

²¹Please refer to [FMV and 24-hour Urine Sampling Flowchart](#).

²²Patients will need to complete a paper diary at home in the 2 days prior to [Flow Chart](#) to record times of trial drug intake. Patients will also need to record start and stop times for 24-hour urine samples in a paper diary before Visit 5 and EOT.

²³ Study medication at Visit 4, Visit 6 and EoT will be taken from the medication kit supplied at the previous visit as there is no dispensing at these visits. At all other visits, study medication should be taken from the kit dispensed at the visit.

²⁴ All AEs, SAEs and AESI will be collected from informed consent until FUp1 (end of residual effect period). Please see [section 5.2.6.2.1](#).

²⁵ After FUp1 until the individual patient's end of trial, the investigator should report any cancers of new histology and exacerbations of existing cancer, all trial treatment related SAEs and trial treatment related AESIs. Please see [section 5.2.6.2.1](#).

²⁶ After the individual patient's end of trial, the investigator does not need to actively monitor the patient for new AEs but should report any occurrence of cancer and trial treatment related SAEs and trial treatment related AESIs of which the investigator may become aware of by any means of communication, e.g. phone call. Those AEs should be reported on the BI SAE form, but not on the CRF.

²⁷ In the case of premature discontinuation during the Randomised Run-in Period, FUp1.1, FUp1.2 and FUp2 do not need to be conducted.

²⁸ At Visits 4 and 5, only compliance to Empagliflozin/placebo will be calculated. At Visits 6, 7, 8, 9 and EOT, compliance will be calculated for both Empagliflozin/placebo and BI 690517/placebo.

²⁹ Days and associated time windows are relative to Visit 5.

FMV AND 24-HOUR URINE SAMPLING FLOW CHART

All samples listed in the following table should be collected by the patient, unless the patient is not able to do it.

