6.2.6 Follow-up period and trial completion

The Follow-up Period is 4 weeks and consists of two visits, FUp1 and FUp2, with two intermediate home sampling timepoints. Please see the [Flow Chart](#) for timelines and visit details. No study medication is taken during the Follow-up Period.

The Residual Effect Period (REP) in this study is 7 days, therefore visit FUp1 should be performed no earlier than 7 days after the End of Treatment Visit.

Other follow up visits and assessments should be scheduled relative to the EoT visit i.e., there will be home sampling without visit at 2 weeks and 3 weeks after EoT, and FUp2 should be 4 weeks after EoT.

Patients who prematurely discontinue during the Run-In Period should have FUp1 as a minimum. Patients randomised to the Treatment Period should be encouraged to complete all visits and procedures in the FUp period. If the patient does not wish to complete all visits or procedures, they should have FUp1 as a minimum.

For patients who prematurely discontinue during the Run-In Period, aldosterone samples do not need to be taken at FUp1 or FUp2.

For patients who have not had [REDACTED] collected at EOT, these samples do not need to be taken at FUp1 and/or FUp2.

Participation in this trial is concluded once FUp2 has been completed. Additional visits may be scheduled for continued safety monitoring after the FUp2 visit if needed in the opinion of the investigator. Abnormal assessments or lab values judged clinically relevant by the investigator will be monitored until they return to a medically acceptable level.

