Run-in	Placebo, Empagliflozin, respectively	Date / time of first administration of empagliflozin / placebo	For patients discontinue in Run-in Period, 12:00 a.m on the day after last administration of empagliflozin / placebo + REP (7 days),

			For patients continue in Treatment Period, 12:00 a.m on the day after last administration of empagliflozin / placebo + REP (7 days) or first administration of BI 690517 / placebo, whichever occurs first
On-treatment	Placebo, BI 690517, Plus Empagliflozin or matching placebo, respectively	Date / time of first administration of BI 690517 / placebo	12:00 a.m on the day after last administration of BI 690517 / placebo + REP (7 days) Or 12:00 a.m on the day after patient's trial termination date,
Follow-up ¹	F/U Placebo, F/U BI 690517, plus Empagliflozin or matching placebo, respectively	12:00 a.m on the day after last administration of BI 690517 / placebo + REP (7 days)	12:00 a.m on the day after patient's trial termination date

¹ Follow-up phase might not exist, e.g. if the patient's trial termination date is within 7 days after last administration of study drug

In the case that the patient is permanently discontinued BI 690517, but is continuing on Empagliflozin during Treatment Period, the occurrence of AEs between REP of BI 690517 and REP of Empagliflozin will be provided in the listing. For treatment interruptions, the occurrence of AEs between the start of interruption and re- start of treatment will be assigned to actual treatment received. These cases will be flagged in the safety listings as occurring during the off-treatment period. AEs will be displayed by dose group and will be provided in the CTR.

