6.7 BASELINE, TIME WINDOWS AND CALCULATED VISITS

Section 2.2.2 of the CTP:

Throughout this protocol, the term “baseline” refers to the last observation prior to the first intake of trial medication, with the exception of FMV urine UACR. Baseline for the FMV urine UACR, is defined as the mean of all available samples from week -2 until prior to the first intake of trial medication. This does not include the UACR measured in spot urine at Screening.

Measurements taken after start of administration of trial treatment of BI 690517 will be considered on-treatment values based on the definition in [Section 6.1](#), and will be assigned to visits for statistical analysis, if applicable, as defined below.

Analysis of AE data, potentially clinically significant abnormal laboratory values, concomitant medication or non-drug therapies, as well as use of rescue therapy will not be based on visits. Therefore, no assignment to time windows will be necessary for such data.

The derivation of the last value, minimum value and maximum value of laboratory and vital signs data will consider all on-treatment values (whether or not selected in any time window; see [Section 6.1](#) for definition of the on-treatment period) within the period of interest; these will be derived for analysis of laboratory and vital signs data.

All other safety and efficacy measurements will be assigned to visits based on extended time windows around the planned visit dates, defined relative to the day of first trial treatment of BI 690517 (which is scheduled for Visit 5).

Repeated and unscheduled efficacy and safety measurements (except for laboratory data) will be handled similarly to scheduled measurements and will also be assigned to a time window depending upon the date of measurement. For handling of laboratory measurements see also [Section 7.8.2](#).

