7.8.2 Laboratory data

The analyses of laboratory data will be descriptive in nature and will be based on BI standards "Handling, Display and Analysis of Laboratory Data" (11). Note that data from the central laboratory will be used for all displays described below, unless otherwise specified.

The analysis of continuous laboratory parameters will be based on normalised values, which means transforming to a standard unit and to a standard reference range. The last assessment before the second randomisation at visit 5 is chosen as the baseline value. The laboratory data at EoT visit are defined as EoT values. In the case that the patient is permanently discontinued BI 690517, but is continuing on empagliflozin during Treatment Period, EoT for analysis of laboratory data will be defined as the nearest scheduled lab visit on treatment of BI 690517.

Descriptive statistics of laboratory values over time and for the difference from baseline (see Section 6.7) will be based upon normalised values and provided by visit, including summaries of the last value on treatment, the minimum and maximum value on treatment.

Laboratory values will be compared to their reference ranges; a shift table will be provided for the number of patients within and outside the reference range at baseline and at the last measurement on treatment. This analysis will be based on standardized laboratory values.

Potentially clinically significant abnormalities will be identified based on BI standard rules which are based on converted values and converted reference ranges using SI lab units. These rules will be listed in the SDL appendix of the CTR. Frequency tables will summarise the number of patients with potentially clinically significant abnormalities.

Patients having an abnormal lab value at baseline will be presented separately. A separate listing will present potentially clinically significant abnormal lab values.

All individual laboratory data will be listed. Values outside the reference range will be flagged. In addition, potentially clinically significant values will be flagged in the listing.

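### The SAP's last on-treatment laboratory value is an on-drug sample or a 7-day off-drug sample, depending on the day of the FUp1 appointment

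*SAP*

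**What the plan says.** - SAP 6.7 classifies measurements by the adverse event phases: "Measurements taken after start of administration of trial treatment of BI 690517 will be considered on-treatment values based on the definition in" Section 6.1. It goes on: "The derivation of the last value, minimum value and maximum value of laboratory and vital signs data will consider all on-treatment values". A value is eligible even if no visit window selected it.
- SAP 6.1, Table 6.1:1, sets out those phases for the analysis of adverse events. The on-treatment phase starts at the first dose of BI 690517 or placebo and ends, exclusive, at "12:00 a.m on the day after last administration of BI 690517 / placebo + REP (7 days").
- SAP 7.8.2 summarises the last, minimum and maximum laboratory values on treatment. Its shift table counts patients "within and outside the reference range at baseline and at the last measurement on treatment". EoT values are defined separately, as those from the EoT visit.
- The protocol has a dose taken at the EoT visit (Flow Chart, footnote 23): "Study medication at Visit 4, Visit 6 and EoT will be taken from the medication kit supplied at the previous visit". In follow-up, "No study medication is taken during the Follow-up Period" (Section 6.2.6).
- On timing, "visit FUp1 should be performed no earlier than 7 days after the End of Treatment Visit" (Protocol 6.2.6). The Flow Chart plans FUp1 for Day 106 with a window of +3 days, and marks safety laboratory, eGFR, serum cortisol and vital signs at that visit.

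No visible text in either document excludes FUp1 from the last on-treatment value.

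**The concern.** A 7-day tail after the last dose is a sensible rule for attributing adverse events. For a last measured value it does something else: it lets a sample taken a week off drug stand in for the patient's state on drug. Here the end of the tail falls on the planned day of a visit with a full safety laboratory, so following the schedule exactly is what triggers the problem.

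The laboratory measures at stake matter for BI 690517. Protocol 1.4.2 lists a mechanism-related potassium rise, and Sections 3.1 and 3.2 anticipate a fall in eGFR. If such a change partly reverses within a week, a shift table and a last-value summary that include FUp1 samples lean towards no drug effect. Which patients contribute an off-drug value is decided by a one-day difference in an appointment.

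**Working it through.** **Inputs.** EoT Day 99, window ±2; FUp1 Day 106, window +3, at least 7 days after EoT (Protocol Flow Chart). Last dose at the EoT visit (Flow Chart, footnote 23). REP 7 days, end of phase exclusive (SAP 6.1).

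**Planned FUp1 day.** 99 + 7 = Day 106, which reproduces the Flow Chart. The protocol's timed-sampling table agrees: drug at 2352:00 h at EoT and a FUp1 sample at 2519:30 h, a gap of 167.5 h.

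**End of the on-treatment phase.** The SAP wording can be parsed in two ways.
- Day after (last dose + 7): (99 + 7) + 1 = Day 107, 00:00.
- (Day after last dose) + 7: (99 + 1) + 7 = Day 107, 00:00.

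Both give the same limit.

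**Classification of FUp1 when the last dose is on Day 99.**
- Day 106: before Day 107 00:00, so on-treatment. FUp1 is the last value.
- Days 107, 108 and 109: follow-up. The EoT sample is the last value. Protocol 6.2 has assessments done before that day's dose, so this sample is taken during daily dosing.

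**All permitted pairs.** With EoT on Days 97 to 101, FUp1 on Days 106 to 109 and a gap of at least 7 days, FUp1 is included for 99/106, 100/107 and 101/108 only. Those are exactly the pairs with a 7-day gap; every gap of 8 days or more is excluded. The number of pairs says nothing about the share of patients, which depends on how sites book the visit.

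**How far off drug.** For empagliflozin the protocol gives a terminal half-life of 10 to 19 h. Over 168 h that is 168/19 = 8.8 to 168/10 = 16.8 half-lives, leaving about 0.22% down to under 0.001% of drug. This concerns drug level, not effect. No half-life for BI 690517 is visible.

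**Size.** Let s be the share of patients whose last value is FUp1 and r the fraction of the laboratory effect that remains at day 7. The retained mean last-value effect is 1 − s(1 − r). Neither s nor r is in the documents, so these figures are purely illustrative:
- s = 0.25: 75% retained at r = 0, 87.5% at r = 0.5, 100% at r = 1.
- s = 0.5: 50%, 75% and 100%.
- s = 1: 0%, 50% and 100%.

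**The case against.** The dates cannot be disputed, but the reach and weight of the point can.

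- **Ambiguity.** SAP 6.7 limits the values to a period of interest that it does not define, and SAP 7.8 summarises safety for the Run-in and Treatment Periods. The protocol's Treatment Period is 14 weeks, and FUp1 belongs to follow-up. SAP 7.8.2 also relies on an internal laboratory-data standard that is not available here and might hold a further rule. Even so, the explicit pointer in SAP 6.7 is to Section 6.1, and a programmer following it would include FUp1.
- **Residual effect.** SAP 6.1 describes the REP as time when drug or pharmacodynamic effects are still likely. That makes total loss of effect by day 7 (r = 0) hard to assume. But Protocol 3.1 treats FUp1 as the end of the REP, and a residual effect does not make an off-drug sample equivalent to an on-drug one.
- **Signals protected elsewhere.** By-visit summaries use the EoT visit, and adding FUp1 cannot remove an on-drug minimum or maximum. Clinically significant abnormalities, potassium threshold counts (Protocol 7.2.6) and special adverse event summaries stand apart from the last value. All safety analyses are descriptive. This stands, and it limits the damage to two laboratory displays.
- **Vital signs.** A reader might infer that blood pressure shift tables are affected too. None is specified. SAP 7.8.3 defines EoT as the EoT visit and counts marked changes at each visit. Only the last value derived under SAP 6.7 is touched.
- **Early stoppers.** A reader might infer that patients stopped for high potassium routinely contribute an off-drug recheck. Protocol Table 4.2.1.1:1 schedules no recheck after permanent discontinuation, and SAP 7.8.2 uses central laboratory data by default, so local rechecks would not normally enter. The most the text supports is that an EoT sample taken within 7 days after an early stop may count as on-treatment.

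**Conclusion.** The point holds for the SAP 7.8.2 laboratory shift table and last-value summary. As written, the rule gives an off-drug last value to a completer whose FUp1 is exactly 7 days after the last dose, and an on-drug value to one seen 8 or more days after it. The displays then understate any laboratory effect that wanes within a week.

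This rests on two assumptions: that SAP 6.7 is applied through Section 6.1 as it directs, and that the unseen laboratory standard does not override it. The direction of the bias is conditional on offset within a week. Its size is not derivable, and a claim that effects are in fact understated by a given percentage would go beyond the documents. Primary efficacy is not affected.

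**What to change.** In SAP 6.7 and 7.8.2, state that follow-up visits (FUp1 onward) are not eligible for the last value on treatment or for the shift-table endpoint. A completer's last value is then the EoT sample, or the last earlier on-drug sample if EoT is missing. Keep the 7-day REP window for adverse events, minimum and maximum values, and potentially clinically significant abnormalities. Show FUp1 as its own off-treatment visit.

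For patients who stop early, keep the EoT-visit sample if it lies within the REP and flag it as off drug. A strict cutoff at the last dose plus one day would be worse: under Protocol 6.2.5 a patient whose stop does not coincide with a visit returns later for EoT, and the cutoff would discard that sample. The last value could then revert to a scheduled visit up to about 28 days earlier (for example Day 71 against Day 99).

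The cost is a short wording change and one derivation flag. The one downside is that the last value and the minimum and maximum use slightly different windows, which a table footnote can state.

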7. PLANNED ANALYSIS

The format of the listings and tables will follow the BI standards "Standards for reporting of clinical trials and project summaries" (6), with the exception of those generated for PK calculations following BI standards for PK/PD analysis (7,8).

The individual values of all patients will be listed, sorted by dose groups of study treatment (empagliflozin/ matching placebo + BI 690517/ matching placebo), patient number and visit (if visit is applicable in the respective listing). AE listings will be sorted by study treatment (see Section 7.8.1 below for details). The listings will be contained in Appendix 16.2 of the CTR.

For end-of-text tables, the set of summary statistics of continuous variables is:

N	number of non-missing observations
Mean	arithmetic mean
SD	standard deviation
SE	standard error (except for PK)
Min	minimum
Median	median
Max	maximum

For plasma concentrations, as well as for PK parameters, the following descriptive statistics will additionally be calculated:

CV	arithmetic coefficient of variation
gMean	geometric mean
gCV	geometric coefficient of variation
P10	10th percentile
Q1	1st quartile
Q3	3rd quartile
P90	90th percentile

The data format for descriptive statistics of plasma concentrations will be identical with the data format of the respective concentrations. The descriptive statistics of PK parameters will be calculated using the individual values with the number of decimal places as provided by the evaluation program. Then the individual values as well as the descriptive statistics will be reported with three significant digits in the CTR.

Tabulations of frequencies for categorical data will include all possible categories and will display the number of observations in a category as well as the percentage (%). Percentages will be rounded to one decimal place. The category missing will be displayed if and only if there actually are missing values. Percentages will be based on all patients in the respective patient set whether they have non-missing values or not.

Units of variables should be given in the titles or column/row descriptors in square brackets (e.g. [mg]).

Exclusion of PK parameters

The ADS ADPP (PK parameters) contains column variables APEXC and APEXCO indicating inclusion/exclusion (APEXC) of a PK parameter and an analysis flag comment (APEXCO). All analyses based on the PKS will include parameters if they are not flagged for exclusion, that is APEXC is equal to “Included”.

Exclusion of PK concentrations

The ADS ADPC (PK concentrations per time-point or per time-interval) contains column variables ACEXC or ACEXCO indicating inclusion/exclusion (ACEXC) of a concentration and an analysis flag comment (ACEXCO). Exclusion of a concentration depends on the analysis flag comment ACEXCO. For example, if ACEXCO is set to ‘ALL CALC’, the value will be excluded for all types of analyses based on concentrations. If ACEXCO is set to ‘DESC STATS’, the value will be excluded from descriptive evaluations per planned time point/time interval. If ACEXCO contains the addition ‘TIME VIOLATION’ or ‘TIME DEVIATION’, the value can be used for further analyses based on actual times. If ACEXCO is set to ‘HALF LIFE’, the value will be excluded from half-life calculation (and, as a consequence, any calculation that relies on λ_z) only; the value is included for all other analyses.

Further details are given in BI-KMED-TMCP-MAN-0014 “Noncompartmental PK/PD analyses of Clinical Studies”.

7.1 DEMOGRAPHIC AND OTHER BASELINE CHARACTERISTICS

Only descriptive statistics are planned for this section of the report. The data will be summarised by dose groups of study treatment, and in total. Disease characteristics during Run-in Period will be based on available data at Screening for randomised run-in set. Baseline characteristics for randomised set will be based on available data prior to the first intake of BI 690517. Additionally, demographic and baseline characteristics will be displayed for DKD and non-DKD populations of the RS, respectively.

